5.1.3.2 Health Coaching Session

Coaches will review the interview output with participants to collaboratively create a coaching plan prioritizing educational and skills-building topics for coaching sessions. At each coaching session, coaches will reassess barriers and facilitators of HIV/STI prevention and deliver indicated risk-reduction counseling. Coaching sessions will focus on generating skills to move participants toward prevention goal attainment by using MI to elicit participant perspectives on prevention needs (such as PrEP initiation) and challenges, and then using ACT to reframe barriers as recognizable dilemmas for which there are effective solutions. Each coaching session will include a brief psycho-educational module about an HIV/STI prevention topic according to the individualized educational plan. The Aim 2 data will determine the optimal method for coaches to communicate prevention goals to the PCP after each session, to ensure appropriate linkage to clinical care.

5.1.3.3 Electronic Medical Record Review

As part of the study, the study team will review the CHOP medical record of the participants for particular variables:

- STI test dates
- STI diagnoses
- STI medications including PrEP
- Mental health diagnoses: derived from the problem list in the general EPIC chart.
 No data will be accessed from protected mental health encounters.

5.2 Efficacy Evaluations

These are the measures that will be used to assess the efficacy of the study intervention

Aim 1: N/A

Aim 2: N/A

Aim 3: The primary efficacy outcome is the difference in change in self-efficacy between baseline and six-month visits for the intervention group versus control, as measured by the modified Generalized Self-Efficacy Scale.

5.2.1 Diagnostic Tests, Scales, Measures, etc.

See the list of CASIs in section 5.1.3.1 above.

5.3 Safety Evaluation

Subject safety will be monitored by adverse events surveillance, reporting and attention to continuous quality improvement to reduce the occurrence of adverse events.

Although the study is minimal risk, it still requires a high level of scrutiny and vigilance with respect to participant safety and data management, particularly given the sensitive nature of the data and enrollment of minor adolescents. At least once every three months, we will review data storage and integrity. We will jointly review and report any unanticipated or adverse events (i.e., breach of privacy) to the CHOP IRB and National Institute of Mental Health (NIMH) in accordance with the NIMH reportable events policy.

For Aim 1, the focus groups and individual interviews contain questions that may make some participants uncomfortable or contain sensitive information. At the beginning of the focus group, we will outline the rules of the group (see appendix), including a statement that participants can opt out of answering any question, that confidentiality will be upheld, and that all opinions will be respected, and that we will use pseudonyms (e.g. favorite superhero, cartoon character, or color) to refer to each other in the group. For the Aim 1 individual interviews, participants will be allowed to opt out of any questions, and the script has been designed to still glean important information about sexual health in primary care, even if a participant does not want to share their own testing experience. In addition, the study team will take additional precautions for those participants completing focus groups or in-depth interviews on a phone or via video conferencing using a HIPAA compliant CHOP approved vendor. We will have two research team members moderating each focus group. The virtual conference rooms will be password protected, and a study team member must admit each participant into the group. Before admitting them to the larger group, a study team member will individually and confidentially confirm the physical location of each participant and their best contact information. Participants will also choose a pseudonym (e.g. favorite superhero, cartoon character, or color) prior to entering the virtual focus group and the moderator will change their screen name to that pseudonym prior to entry.

For Aim 3, all participants will be patients of CHOP primary care clinics, and thus can be rapidly referred to clinicians and social workers in case there is a need to intervene for an identified mental health issue. Our mood rating instrument, the PSC-17, does not include any assessment of suicidal ideation. However, if a participant discloses suicidal ideation, homicidal ideation, or abuse during an intervention session, the PI will be notified immediately, as well as the clinic social worker. Based on clinician assessment, participants who report suicidal ideation will be referred to the local Emergency Department or psychiatric crisis center, as needed. Any reports of child abuse will be reported to the clinic social worker and reported to ChildLine in accordance with Pennsylvania State Law. All participants will be provided mental health resources at the end of the first session, irrespective of their score on the PSC-17.

Participants will complete a modified version of the Adverse Childhood Experiences survey. To minimize the risk to participants that may arise regarding fear of disclosing a specific form of adversity, the study will utilize a modified version of the ACES questionnaire that has been validated in middle and high school students. The modified inventory is presented in 7 items. Within each item, participants are presented with a diagram including 2-4 circles. Each circle contains the description of an ACE, with language adapted from the cited inventories. The wording has been modified to be appropriate for the reading and comprehension abilities of 14 to 18-year-olds. Participants are instructed to read the ACE description contained in each circle, to think back on their entire life, and to decide if the

ACE described within the circle applies to them. Youth respond to each item on the inventory by indicating how many circles (0- 4) in that item apply to them. The modified ACE inventory allows the investigators to calculate a conventional ACE score (in keeping with the extant literature). Because this is a validated scale, we must include all questions to come up with a composite score. However, participants do not have to answer any question they feel uncomfortable with. There is a great deal of literature about the connection between ACES and STI diagnoses.²⁵⁻²⁹ The data from the ACES questionnaire will be used to determine whether the final health coaching intervention needs to be modified to contain trauma-focused elements. Lastly, substance abuse will be measured by the CRAFFT which contains opening questions frequency of substance use, followed by questions regarding specific negative consequences of substance abuse. A score >4 on the CRAFFT is suggests substance dependence. Participants with CRAFFT scores >4 will be given a list of resources for substance treatment and referred back to their PCP.

ACES questionnaire

There are some questions included in the ACES questionnaire that probe about sensitive information related to prior childhood trauma. While participants are informed that they may refuse to answer any questions at any time, responses or reactions to certain questions may indicate potential distress on the part of the participants. If at any time during the assessment or completion of the questionnaires, a participant divulges to any study staff that he or she is at risk for harm, including but not limited to being abused or experiencing violence, if harm is suspected or likely, or if the participant indicates he or she is suicidal/homicidal, a member of the subject's primary care team or a study physician will be notified. This primary care team member or study physician will come speak directly in-person or over the phone with the subject at that time. They will determine clinical risk and follow up, which may include referral to one of the onsite primary care social workers or a local crisis center.

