4.2 Study Intervention Phase

Aim 1: No intervention

Aim 2: No intervention

Aim 3: The discussion of the intervention phase is strictly for Aim 3 of the study project.

For the Aim 3 RCT phase, the participants randomized to the standard of care group will not undergo the health coaching intervention. The participants randomized to the health coaching group will attend health coaching sessions at the baseline, 1-week, 1-month and 3-month visits.

4.2.1 Follow up Visit 1

Aim 1: N/A

Aim 2: N/A

Aim 3: Both the health coaching group and the standard of care group will complete follow-up surveys at the 6-month follow-up visit.

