5.1.1.1 Focus groups or In-depth interviews

Five audio recorded in-person, or video recorded virtual focus groups will be conducted ~50 participants, 5-8 per group.

Focus groups and in-depth interviews will identify HIV/STI prevention barriers and facilitators and preferences for an intervention format across different demographic populations of adolescents. We will conduct separate focus groups for the following populations: cisgender females, heterosexual males and YMSM/TW, and a mixed sex/sexual orientation group of adolescents with identified depression on their annual primary care screening. Participants will have the option to complete an in-depth interview if they wish to not participate in the focus group, as described in section 4.1. Identifying key content themes and delivery preferences among different demographic groups and youth with mental health conditions will allow for enhanced tailoring of content for different adolescent user groups. For example, if youth with depression are more likely to identify medication self-efficacy as a barrier to PrEP uptake, intervention content can be tailored for this population to emphasize PrEP adherence strategies.

Focus groups will occur in-person, or if necessary, via virtual video conferencing using a HIPAA compliant CHOP approved vendor. Focus groups will start with an informational session on HIV/STI prevention strategies (PrEP, condoms, HIV/STI testing, and partner notification). We will then facilitate the focus group to identify the most salient barriers/ facilitators for each prevention strategy within each focus group. In the second half of the focus groups, we will focus on adolescent preferences for the delivery of sexual health care, and delivery of the proposed intervention. Youth will then share their preferences. Focus groups will last 1-2 hours. The individual in-depth interviews will occur in-person, via

phone, or video conferencing using a HIPAA compliant CHOP approved vendor. These interviews will focus on youth preferences for sexual health care in primary care, using the participant's own prior sexual health encounters in primary care as the framework for the interview. Given the sensitive nature of the topic, youth have the option to opt out of any of the interview questions (see appendix). In-depth interviews will last 30-45 minutes.

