The primary outcome for the RCT is the change in prevention self-efficacy between intervention and control conditions between the baseline and six-month (final) visits. We will compare the exposure variable of treatment group with the outcome variable of continuous score on the modified Generalized Self-Efficacy Scale at baseline, intermediate (e.g. three month), and six-month visits using mixed effects logistic regression models with a random intercept for patient and a random slope for time. In exploratory analyses, to determine if the mental health predictors impact the self-efficacy outcome, we will create separate mixed effects regression models to compare self-efficacy score for those with and without mood ratings consistent with depression on the PSC-17, high trauma (Adverse Childhood Experiences Scale score >4 vs not), and substance abuse (CRAFFT score >4) adjusting for treatment group and demographic characteristics including sex. In order to assess the impact of STI timing on the primary outcome of prevention self-efficacy, we will use linear regression models and days between STI diagnosis and the first coaching visit in the intervention group, adjusting for demographic covariates including sex and sexual orientation. Finally, we will assess if coaching may have a significant effect on other domains in the self-efficacy pathway of our model, by repeating the primary analysis above with scores for the Patient Activation Measure [PAM], and Confidence in Safer Sex Scale.

There will be no adjustment of p value for multiple comparisons given the exploratory nature of these analyses.

Secondary outcome analyses:

- Referral feasibility: Calculated as the number of potential participants referred to study staff over the number of patients with bacterial STI at the clinics during the study period. This denominator will be identified using the CHOP STI dataset.
- Recruitment feasibility: Calculated as the number of patients enrolled over the number of patients referred.

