We will establish protocols to address potential disclosure of sensitive information to study team members (i.e. depression, substance abuse or intimate partner violence). In addition, protocols will be established to address any psychological distress on the part of participants during the course of data collection, involving existing clinical providers and social workers to evaluate and provide appropriate resources to the participant as appropriate. During the course of the study, research data will be stored in password protected files on secure servers in accordance with CHOP policy. We will be responsible for ensuring that all study team members understand the requirements for data storage and protection. All completed study documents will be stored in locked cabinets, and all computer-entered data will be stored and analyzed on password-protected computers at CHOP. Access to documents and data will be limited to myself and members of my research team. We will be responsible for ensuring that all those with access to the information understand the requirements for use of the data on password protected computers and servers. Any transfer of data between members of the research team will be done through CHOP's encrypted file sharing system.

In addition, during the randomized controlled trial in Aim 3, we will conduct routine monitoring of data throughout the study to ensure data is collected and recorded in adherence to the research plan, and that confidentiality of participants is maintained. As this is an experimental study, it requires a high level of scrutiny and vigilance with respect to participant safety and data management, particularly given the sensitive nature of the data and enrollment of minor adolescents. At least once per month during Aim 3 data collection and analysis, we will review data storage and integrity and jointly review and report any unanticipated or adverse events (i.e. breach of privacy) to the CHOP IRB and NIMH in accordance with the NIMH reportable events policy.

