9.4.2 Risk Assessment

Aim 1: Risks to participants are anticipated to be minimal. There is a minor risk of unauthorized disclosure of PHI, which will be made known to participants. There is a risk of loss of confidentiality due to using video conferencing, however, the study team will take additional precautions for those participants completing focus groups or in-depth interviews on a phone or via video conferencing using a HIPAA compliant CHOP approved vendor. We will have two research team members moderating each focus group. The virtual conference rooms will be password protected, and a study team member must admit each participant into the group. Before admitting them to the larger group, a study team member will individually and confidentially confirm the physical location of each participant and their best contact information. Participants will also choose a pseudonym (e.g. favorite superhero, cartoon character, or color) prior to entering the virtual focus group and the moderator will change their screen name to that pseudonym prior to entry. Risks will be greatly reduced by the data protection procedures in section 8.2 above.

Aim 2: There is a minor risk of unauthorized disclosure of confidential information, which will be made known to participants.

Aim 3: Risks to participants are anticipated to be minimal. Coaching sessions will be administered by trained coaches in a confidential setting to avoid emotional discomfort to participants when discussing sensitive matters. There is minor risk of variance in the quality of coaching content, but this will be avoided due to extensive training provided to the coaches in accordance with the Motivational Interviewing Network of Trainers training system. Coaching sessions will be continuously reviewed for quality and fidelity to the treatment protocol. There is the minor risk that the CASIs may uncover previously undiagnosed depression or substance abuse. There is a minor risk of unauthorized disclosure of confidential information, which will be made known to participants.

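### Section 5.3 attaches a PCP referral to a high CRAFFT score but no referral to a PSC-17 score in the depression range, although section 9.4.2 says the surveys may uncover either condition

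*Combined protocol and SAP*

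**What the plan says.** Section 9.4.2 (Aim 3) names the risk: "There is the minor risk that the CASIs may uncover previously undiagnosed depression or substance abuse". Section 5.3 then treats the two conditions differently.

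- **Substance abuse:** "Participants with CRAFFT scores >4 will be given a list of resources for substance treatment and referred back to their PCP".
- **Depression:** "All participants will be provided mental health resources at the end of the first session, irrespective of their score on the PSC-17". The same paragraph says that Aim 3 participants, being CHOP primary care patients, can be sent quickly to clinicians or social workers once a mental health issue has been identified. It also notes that the PSC-17 does not ask about suicidal ideation.

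The stated use of the PSC-17 score is analytic. Section 6.3.2 compares self-efficacy between "those with and without mood ratings consistent with depression on the PSC-17", and uses a high-depressive-symptom group again in the retention analysis. No numeric cut-off is given.

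Other safeguards are stated. In 5.3, "if a participant discloses suicidal ideation, homicidal ideation, or abuse during an intervention session, the PI will be notified immediately". The ACES paragraph of 5.3 brings in a clinician if, during any questionnaire, a participant tells staff of a risk of harm or harm is suspected. Section 7.1 directs standard-of-care (SOC) participants to their PCP for clinical issues after baseline. Section 9.4.1 promises protocols, still to be established, for sensitive disclosures to staff (depression is one of its examples) and for distress during data collection.

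**The concern.** The team will hold a mood score on each adolescent, some as young as 13, and will use it to label some of them as depressed for analysis. The plan does not say that anyone must tell the participant or offer a referral because of that score. It does say so for the other condition in the same risk statement, so a score-based referral was evidently thought workable in this trial.

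At stake is participant safety, not the validity of the primary comparison. Someone could report marked depressive symptoms on a self-entered survey, disclose nothing aloud, receive the same resources as everyone else, and have no individual follow-up. A participant with a CRAFFT score above 4 would be referred.

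**Working it through.** The plan states no figure to reproduce. The check is textual, followed by a rough count for workload.

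**Step 1: the two instruments side by side**

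| | CRAFFT | PSC-17 |
|---|---|---|
| Condition named in 9.4.2 | Substance abuse | Depression |
| Resources (5.3) | Those scoring above 4 | Everyone |
| Referral that follows from the score (5.3) | To PCP, above 4 | None stated |
| Group used in 6.3.2 | Above 4 | Depression range, cut-off not given |

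For the CRAFFT, the analysis cut-off and the safety cut-off coincide. For the PSC-17, the plan implies an analysis cut-off and has no safety counterpart. On resources the PSC-17 provision is the broader of the two. The difference is one element: the referral.

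**Step 2: what each other safeguard acts on.** Take a participant who scores in the depression range and says nothing.

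- Rapid referral (5.3) acts on an identified issue. The text does not say that a score identifies one.
- PI notification (5.3) acts on disclosure in an intervention session.
- The questionnaire rule (5.3, ACES paragraph) acts on risk divulged or harm suspected. With no suicidality item, a high PSC-17 score need not signal either.
- PCP referral of SOC participants (7.1) acts on clinical issues that arise. The text does not say that the score reaches the PCP.
- Chart review (5.1.3.3) reads diagnoses already on the problem list and sends nothing back.
- Usual-care screening may already have found some cases. Section 5.1.1.1 describes an Aim 1 group with "identified depression on their annual primary care screening".
- The 9.4.1 protocols, as described, act on disclosure to staff and on distress.

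None is stated to act on a PSC-17 score. Surveys are self-entered by default (5.1.3.1) and the baseline survey can be sent as a link (9.7), so staff may observe nothing.

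**Step 3: later visits.** Section 5.1.3.1 lists the Youth Pediatric Symptom Checklist under surveys for baseline, 3 and 6 months. If it is repeated, a participant who first scores in range at 3 or 6 months falls after the one stated distribution of resources.

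**Step 4: size.** Inputs: n = 150 (3.3.2 and 6.4); a pilot recruitment aim of 10 in one month (3.3.1); proportion in range p, assumed 10%, 20% or 30%.

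- People in range at baseline = 150 × p: 15, 30 or 45.
- Recruitment at the pilot pace: 150 / 10 = 15 months.
- Baseline contacts per month: 15/15 = 1, 30/15 = 2, 45/15 = 3.

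A faster pace would raise the monthly count in proportion and leave the total unchanged. The total includes false positives and people whose depression is already known; the documents give no way to separate them.

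**The case against.** The strongest reply is that the universal provision is deliberate and in one respect more protective than the CRAFFT rule, because nobody has to cross a threshold to receive resources. That stands, and the provision should stay.

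A second reply is that the rapid-referral sentence comes immediately before the PSC-17 is introduced, so a high score is naturally read as one way of identifying an issue. That reading is reasonable but not written down, and the next statement about the score is that it makes no difference to what is given. The route exists; what is missing is the link from score to route.

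A third reply is that the 9.4.1 protocols may already contain the rule. They are not among the documents, so this cannot be excluded. If they do, a cross-reference is enough.

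A reader might go further and infer that the SOC arm is left unprotected, since PI notification is tied to intervention sessions and "the participants randomized to the standard of care group will not undergo the health coaching intervention". The documents do not support that. The questionnaire rule in 5.3 is not limited by arm and does not require verbal disclosure if harm is suspected, 7.1 directs SOC participants to their PCP after baseline, and both arms return to clinic at 3 months for STI testing. The missing score-based step is common to both arms.

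**Conclusion.** The point holds in a narrow form: for Aim 3 the plan states no referral that follows from a PSC-17 score in the depression range, while it does for a CRAFFT score above 4, and it names both conditions as ones the surveys may uncover. It is a shortfall in participant safety as the plan is written, and a cheap one to close.

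Two stronger conclusions might be drawn, and neither is supported. The plan does not lack a mental health response: it provides resources to all, a referral route, escalation on disclosure or suspected harm, and promised protocols. Nor does it contradict itself: it responds unequally to two named risks.

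The finding rests on the text alone. The count of 15 to 45 people, about 1 to 3 a month at baseline, rests on an assumed 10% to 30% in range and on RCT recruitment matching the pilot's target pace. It indicates workload and is not an estimate of missed cases.

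**What to change.** Keep the resources for everyone and add one sentence to 5.3 after the PSC-17 statement:

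> In both arms, at each visit where the PSC-17 is completed, participants who score in the depression range (the cut-off used in 6.3.2, or one set by the clinical investigators) will be told so confidentially and offered referral to their PCP or clinic social worker, as for CRAFFT >4.

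If the 9.4.1 protocols already contain this rule, cite them in 5.3 instead. Parity with the CRAFFT rule needs no automated alert, mandatory physician contact or log of refusals, and section 8.2 already provides for tracking referrals in REDCap.

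The costs are some false-positive contacts, within the roughly 1 to 3 a month at baseline under the assumptions above plus any at later visits, and a confidentiality cost for minors who consent without a parent (9.6), given the limit in 9.3 on sharing health information outside the research team. Offering referral instead of imposing it limits the second cost. The rule is the same in both arms.
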